Subject recruitment will be coordinated through [name] ongoing studies. The availability of recruitment infrastructure, trained clinical interviewers, and cognitive remediation software will greatly facilitate the launch and conduct of the project. All subjects interested in the study will be prescreened for general inclusion and exclusion criteria by the recruiter using HIPAA compliant procedures. During the first visit (approximately 2 hours), participants will be consented and receive standardized clinical interviews to ensure diagnosis and eligibility. Participants will also receive symptom ratings of general psychiatric and negative symptoms, as well as mood symptoms. Subjects who fit selection criteria for the study will be scheduled for another visit, within 1 week of their first visit. During the second visit, (approximately 3.5 hours), subjects will be administered a comprehensive battery of cognitive, electrophysiological, and functional capacity/community functioning measures. Subjects will then be randomly assigned to one of the two cognitive remediation treatments (BFP and Cogpack) or to the control treatment (see randomization and treatment procedure below). Subjects will participate in 3 treatment sessions a week (1 hour each) for 12 weeks. After 18 treatment sessions, subjects will come back for a midpoint assessment visit (1.5 hours) in which they will be administered the electrophysiological measures again and two brief questionnaires. Upon completion of treatment, subjects will be scheduled for a post-treatment visit within 2 weeks of the last treatment session. This visit will last approximately 3.5 hours and will include the same clinical, cognitive, electrophysiological, and functional capacity/community functioning assessments that were administered prior to treatment. A urine toxicology screen will be conducted as part of each assessment visit. In the rare instance when a subject tests positive on the urine toxicology screen, he/she will be rescheduled to come back on a different day to complete the assessments. Overall, the study will consist of 4 visits (11 hours total) and 36 treatment sessions (36 hours total). Subjects will be compensated \$15/hour for the interview and testing sessions (first 2 visits, mid- and post-training visits) and \$10/hour for the treatment sessions, a rate deemed acceptable by our IRB. Funding is requested for four years of data collection (see Table 1). The IRB application will be prepared prior to the grant being funded.

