Recruitment will be ongoing and we expect to enroll 30 subjects/year. Based on dropout rates in our previous training intervention studies, we project 20% attrition, which will leave us with an estimate of 96 completers: 38 getting BFP training, 38 getting Cogpack training, and 19 getting the control intervention. We will make every effort to hold patients in the study protocol while emphasizing that their participation is strictly voluntary and that they can withdraw at any time. To minimize attrition, we will inform subjects that they will be in the study up to 17 weeks and ensure that they will not be leaving town or relocating during the study period. We will contact those who opt to discontinue treatment to request that they participate in a final outcome assessment. Details of the plan for handling missing data and minimizing potential threats to randomization caused by differential dropout rates are further described in the data analysis section.

Subjects

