The paradigm will involve assessment of visual evoked potentials (VEPs) before and after exposure to tetanizing visual high frequency stimulation (HFS). While maintaining focus on a central fixation cross, subjects will view visual stimuli presented centrally against a white background on a computer monitor located 57 cm in front of them. Each 2-minute VEP assessment block will consist of a pseudorandom oddball sequence of 90% standard (circle) and 10% target (square) stimuli (duration 33 msec) presented at ~ 0.83 Hz (1216 msec mean SOA, range 1075-1340 msec). Subjects will be asked to respond to the target square with a right-handed button press. VEP assessment blocks will be administered 4 minutes (baseline-1) and 2 minutes (baseline-2) before HFS and 2 minutes (post-1), 4 minutes (post-2), and 20 minutes (post-3) after HFS. The 2-minute HFS block designed to induce potentiation will consist of repeated presentation of the standard circle at ~ 8.87 Hz (113 msec mean SOA, range 99-116 msec), a rapid flicker rate below the perceptual fusion threshold. Subjects will be administered the auditory MMN paradigm (described below) in the interval between the post-2 and post-3 VEP blocks.

Mismatch Negativity (MMN) Paradigm

A passive auditory oddball paradigm will be used to assess basic auditory processing. Subjects will be presented with standard and duration-deviant tones binaurally using foam ear inserts (1 kHz 85 dB sound pressure level, with 10 ms rise/fall) with a fixed stimulus onset asynchrony of 500 ms, using E-Prime 2.0 (Psychology Software Tools, Inc., Pittsburgh, PA). Standard (90% probability; 50 ms duration) and deviant (10% probability; 100 ms duration) tones will be presented in a fixed, pseudorandom order (with the restriction that at least 4 standard tones are presented between deviant tones). Two-thousand total trials will be administered. During the 25-minute EEG recording,

subjects will be instructed to watch a silent movie to divert attention from the stimuli. The EEG session (including electrode placement and recording) will last approximately 45 minutes.

EEG Processing

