The experimental design for this study is a 3-group randomized clinical trial, with assessments at baseline and the 12-week treatment endpoint. The aims correspond to comparisons of the effects of two active treatments to each other and to a control condition on neurocognition, EEG, and functional capacity. For each of these domains, we specify a primary outcome measure. For neurocognition we will use a composite score created by averaging the t-scores for the 6 neurocognitive domains of the MCCB. The main EEG measure will consist of the MMN amplitude at electrode Fz. For functional capacity we will use the total score from the UPSA. If significant treatment effects are found on any of the primary outcomes, we will perform secondary analyses on the corresponding components or subscale scores to determine whether the results are driven by particular aspects of the main constructs. To further characterize the treatment response profiles, exploratory analyses will be performed to examine the effects of the interventions on composite scores of social cognition and community functioning. We are well aware of the risk of Type I error inherent in a study with a large battery of assessments and have protected against it by clearly specifying a limited a priori set of primary outcome measures and contrasts of interest and designating all others as exploratory. However, since this is a preliminary study, designed to obtain estimates of treatment effects and to identify optimal intervention components and measures for a future definitive efficacy study, it is equally important not to miss any potentially relevant outcomes. All results will therefore be reported using an uncorrected two-sided significance level of $\alpha=.05$.

Prior to performing the primary analyses, descriptive statistics and graphical summaries will be obtained for all outcomes to check for missing data, outliers and the need for transformations or non-parametric methods. To assess the success of randomization, ANOVAs and chi-square tests will be used to test for baseline group differences on the primary outcomes as well as on demographic (age, gender, parental/personal education) and clinical (medication, duration of illness, and symptom severity) characteristics. Measures that show significant differences will be included as covariates in subsequent analyses. Below we give a detailed description of the analytic plan by specific aim.

Analysis Plan By Specific Aim:

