Specific Aim #1: To compare the treatment effects of bottom-up training (BFP) to top-down training (Cogpack) as well as to a control condition on neurocognition.

Specific Aim #2: To compare the treatment effects of bottom-up training (BFP) to top-down training (Cogpack) as well as to a control condition on EEG (MMN).

Specific Aim #3: To compare the treatment effects of bottom-up training (BFP) to top-down training (Cogpack) as well as to a control condition on functional capacity.

Exploratory Aims: 1) To compare the treatment effects of bottom-up training (BFP) to top-down training (Cogpack) as well as to a control condition on social cognition and community functioning and 2) to assess whether changes in MMN are associated with changes in cognition and functioning.

Primary Analyses: To make the most efficient use of our data, our primary analytical technique will be the general linear mixed model (GLMM). GLMMs account for correlations induced by repeated measures within subjects, allow for both fixed and time-varying covariates and automatically handle missing data, producing unbiased parameter estimates provided that observations are missing at random. This allows us to include all available data from all subjects in the analyses, regardless of the degree of study participation or treatment dosage received, consistent with the intent to treat framework. For each of our primary outcomes (MCCB neurocognitive composite for Aim1, MMN amplitude at Fz for Aim 2, UPSA total score for Aim 3), our core model will include group (BFP, Cogpack, control) as the between subject factor, time (baseline, end of treatment) as the within subject factor, and a group by time interaction. Our primary hypotheses correspond to the group by time interactions comparing the outcome trajectories for the two active treatments, which can be obtained as post-hoc contrasts. Such contrasts can also be used to compare each of the active

treatments to the control condition, to test for within group change and to examine the magnitudes of group differences at the end of treatment.

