Exploratory Analyses: Significant results for the primary global measures will be followed by equivalent models for the component subdomain scores to identify the primary drivers of treatment effects. Parallel models will also be fit for the exploratory analyses of social cognition and community functioning measures. To examine the relationships between MMN and cognition and functioning, we will add this EEG index as a time-varying covariate to the primary GLMM models for the other outcome domains. Although we are underpowered for a full mediation analysis, this will also allow us to obtain a preliminary indication of whether treatment effects operate through their effect on electrophysiology. Given that age, duration of illness, symptom severity, medication (indexed by CPZ units) and dosage of treatment (number of sessions) may all impact treatment response, we will also add these measures and their interactions with treatment group and time to the primary models to (i) determine whether they explain additional variation in the outcomes and (ii) obtain preliminary information about potential treatment moderators.

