Attrition and Missing Data: We plan an intent-to-treat approach, using all available data from all subjects, regardless of the degree of program participation. As noted above, our GLMM models automatically handle missing data, making the most efficient use possible of available measurements. However, with this study population there is likely to be moderate data loss (up to 20% due to attrition and EEG artifacts based on our prior experience) and we recognize the potential for bias due to differential dropout. The impact of attrition will be evaluated by comparing dropout rates in the treatment arms using chi-square tests, and by comparing baseline characteristics of dropouts with those who have outcome data. If there is evidence that attrition patterns might introduce bias into the analyses, we will perform supplementary analyses adding propensity-score adjustments to the primary models. In the propensity score framework, baseline characteristics are used to develop a predictive model for attrition (e.g., via logistic regression), and the probability of dropout is used either as a covariate or to weight the observations in the subsequent models. In essence, cases who are similar to dropouts are weighted more heavily to “make up” for others like them who dropped out. As noted above, we will also explore treatment dosage as a covariate in secondary models. Finally, scattered missing data on covariates will be handled using multiple imputation procedures.

Power Considerations

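### MMN is recorded at a midpoint visit, but neither the Aim 2 model nor the attrition model uses it, so missing-at-random is conditioned on less than is observed

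*Combined protocol and SAP*

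**What the plan says.** Research Design and Methods schedules, after 18 treatment sessions, a "midpoint assessment visit (1.5 hours) in which they will be administered the electrophysiological measures again and two brief questionnaires". MMN belongs to that EEG session. The section on the visual long-term potentiation paradigm states: "Subjects will be administered the auditory MMN paradigm", placing it between two of the visual blocks. EEG Processing names MMN amplitude at Fz as the primary EEG outcome. The Aim 2 outcome is therefore due at three visits.

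The statistical sections describe two:

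- Statistical Plan: a "3-group randomized clinical trial, with assessments at baseline and the 12-week treatment endpoint".
- Primary Analyses, for all three primary outcomes with MMN named: "time (baseline, end of treatment) as the within subject factor, and a group by time interaction". Unbiasedness is claimed on condition that data are missing at random.
- Exploratory Analyses, on MMN as a predictor: "we will add this EEG index as a time-varying covariate to the primary GLMM models for the other outcome domains". Those outcomes have no midpoint value.
- Attrition and Missing Data: "baseline characteristics are used to develop a predictive model for attrition". Dropouts are also compared with others on baseline characteristics. The same paragraph describes the mixed model as "making the most efficient use possible of available measurements" and expects up to 20% loss from attrition and EEG artifacts.

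Randomization and Treatment Procedure adds a safeguard: "We will contact those who opt to discontinue treatment to request that they participate in a final outcome assessment".

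**The concern.** A midpoint record cannot enter a model whose time factor has two named levels. A patient with baseline and midpoint EEG but no usable endpoint EEG contributes only the baseline value to Aim 2. That conflicts with the stated intention to use all available data.

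It also makes the missing-data assumption stronger than it need be. In the two-visit model, loss of the endpoint value must be unrelated to MMN given baseline, arm and any added baseline covariates. With the midpoint in the likelihood, loss may also depend on midpoint MMN. The plan itself recognizes possible bias from differential dropout, but its checks do not reach this mechanism. Loss rates can be equal in the two arms while the reasons for loss differ, and then the chi-square test has nothing to detect. A baseline-only propensity model cannot adjust for a post-baseline predictor. The bias would fall on the comparison that the plan calls primary.

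**Working it through.** **Inputs from the plan.** 48 patients per active arm; 20% loss (38.4 per arm with endpoint, which the plan rounds to 38); within-subject correlation r = .7; d = .5 at endpoint and 0 at baseline; two-sided alpha .05.

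**Inputs assumed.** Correlation between adjacent visits from .70 (equal correlations) to √.7 = .837 (decaying with time), with baseline-to-endpoint r kept at .7. The dropout mechanisms below are also assumed, because the documents give none. Outcome SD is 1.

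**1. The plan's own figure.** SD of change = √[2(1 − .7)] = .775. With 38 per arm, SE = .775 × √(2/38) = .178. Power = Φ(.5/.178 − 1.96) = 80.3%. The stated power is reproduced, and it describes a two-visit analysis.

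**2. Precision without the midpoint.** The likelihood estimate of endpoint change in one arm has variance (1 − r²)/38.4 + (1 − r)²/48 = .51/38.4 + .09/48 = .01516. The contrast SE is √(2 × .01516) = .174 and power is 81.9%.

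**3. Precision with the midpoint for everyone lacking endpoint.** Let b1 and b2 be the coefficients of endpoint on baseline and midpoint, and s² the residual variance. The variance is s²/38.4 + Var[(b1 − 1)·baseline + b2·midpoint]/48.

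- Adjacent r = .70: b1 = b2 = .412 and s² = .4235. Variance = .4235/38.4 + .1765/48 = .01471, a fall of 3.0%. Power is 83.0%.
- Adjacent r = .837: b1 = 0, b2 = .837 and s² = .30. Variance = .30/38.4 + .30/48 = .01406, a fall of 7.2%. Power is 84.6%.

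If only half of those lacking endpoint have a midpoint EEG, the variance is .01491 or .01455 (falls of 1.7% and 4.0%; power 82.5% and 83.4%). If none do, there is no gain.

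**4. Bias.** Two million simulated patients; logistic loss in one arm only, with the intercept set for 20% loss; odds ratio (OR) per SD of the change from baseline. Absolute bias of the contrast is shown for adjacent r = .70 / .837.

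| Loss depends on | Two visits | Three visits |
|---|---|---|
| Midpoint change, OR 2, all loss late | .035 / .057 | 0 |
| Same, half the loss early or from artifacts | .020 / .032 | 0 |
| Same, half recovered by the final assessment | .016 / .025 | 0 |
| Midpoint change, OR 4.5, all loss late | .063 / .102 | 0 |
| Midpoint change, equally in both arms at equal rates | 0 | 0 |
| Endpoint change, OR 2 | .085 / .086 | .072 / .052 |

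Reversing the slope reverses the sign.

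**5. A second specification.** Here loss depends on the midpoint value rather than the change, at 20% in both arms, with half the effect assumed present at midpoint. For a true .50:

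- Log-odds slope of −1 per SD in one arm: the two-visit estimate is .54–.55.
- Slopes of −1 and +1 in the two arms: .58–.60.
- Slopes of −2 and +2: .62–.66.

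The three-visit estimate is .50 in every case. In the −1 and −1/+1 cases, weighting by a baseline-only dropout model still gives .54–.60.

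**The case against.** The strongest reply concerns weight, since the omission is plain on the text.

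- **The mechanism is not documented.** Nothing in the plan suggests that loss follows midpoint MMN differently by arm. The Background section describes MMN as automatic and preattentive, so any link to leaving the study would probably be indirect. This stands: the odds ratios are assumptions, and the bias may be zero.
- **The bias is small.** A bias of .03–.06 is 0.17–0.34 of the SE (.174), and moves a nominal 5% test to about 5.3–6.4%. The strong case, .10, gives about 8.9%. The 20% loss is the plan's upper figure; at 10% loss the smallest bias under the second specification is about .02. This also stands.
- **The documented amplitude-related loss is of another kind.** EEG Processing accepts a response only if it is at least twice the prestimulus activity. That loss depends on the same visit's amplitude and can also delete the midpoint value. With the rule assumed to act alike in both arms and about 20% invalid per visit, bias moves only from −.016 to −.015 or from −.015 to −.011 at OR 2, and from −.051 to −.048 or from −.050 to −.041 at OR 4.5. The midpoint does little for this mechanism.
- **Sessions attended enter secondary models.** This is a post-baseline variable related to dropout, but it does not stand in for midpoint MMN and leaves the primary model as it is.
- **A two-visit contrast is a legitimate choice for a preliminary study.** True, but the plan neither says that midpoint MMN is set aside nor why, and it claims the most efficient use of the data.

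These points limit the benefit. None shows the two-visit model doing better; in every scenario examined the three-visit model did at least as well.

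**Conclusion.** The concern holds. MMN at Fz is scheduled at three visits, and the stated Aim 2 model and attrition model ignore the middle one. The omission is certain from the text; the size of its effect is not. Under an assumed 20% loss related to midpoint change in one arm only, the two-visit bias on d = .5 is .03–.06 at an odds ratio of 2 and .06–.10 at 4.5, in either direction. It is .02–.03 if half the loss is early, artifactual or recovered, and zero if the relation is absent, or the same in both arms at equal rates. The three-visit zero applies where loss depends on MMN values actually observed; where loss depends on endpoint change or on the validity rule, some bias remains. The precision gain is at most 7% of variance. Only Aim 2 is affected, and the stated power figures are not wrong. The change should be made because it weakens a doubtful assumption for a primary outcome at almost no cost. It is not a fatal flaw.

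**What to change.** For Aim 2 only, fit MMN at Fz with three time levels (baseline, midpoint, end of treatment) and an unstructured covariance. Keep the baseline-to-endpoint BFP-versus-Cogpack contrast as the primary test. Correct the design sentence in the Statistical Plan to list the midpoint EEG. Add midpoint MMN, where available, to the attrition model for MMN. Aims 1 and 3 keep two levels, because MCCB and UPSA are not scheduled at midpoint. If leaving the midpoint out is deliberate, the plan should say so and give the reason.

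The cost is SAP wording and a few more covariance parameters. No visit is added, and the estimand and the basis of the power calculation are unchanged.

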To assess neurocognitive functioning, the MATRICS Consensus Cognitive Battery (MCCB; [54]) will be administered. The tests in the MCCB were selected from over 90 nominated tests and represent 7 separable cognitive domains [55, 56]. The MCCB takes approximately 60 minutes to administer and provides normed scores, including a summary score and cognitive domain scores. The MCCB includes one social cognition domain (the Managing Emotions component of the MSCEIT) which will not be included in the summary score but rather incorporated into a social cognitive composite score (see below). The remaining 6 domain t-scores from the MCCB will be averaged to create a composite score representing basic cognition as has been done previously [43]. Table 2 shows the tests that comprise the battery and the 6 cognitive domains they represent. The MCCB composite score will serve as the primary cognitive outcome measure. The individual MCCB domain scores will be used in secondary analyses to determine whether an overall effect is driven by any particular aspect of neurocognition.

Table 2: MCCB Cognitive Domains and Tests

Domain Assessed	Measure
Speed of Processing	Trail Making Test (TMT): Part A Brief Assessment of Cognition in Schizophrenia (BACS): Symbol Coding Category Fluency: Animal Naming
Verbal Memory	Hopkins Verbal Learning Test–Revised (HVLt-R)
Visual Memory	Brief Visuospatial Memory Test–Revised (BVMT-R)

Working Memory	Wechsler Memory Scale–Third Edition (WMS-III): Spatial Span Letter–Number Span (LNS)
Attention / Vigilance	Continuous Performance Test–Identical Pairs (CPT-IP)
Reasoning and Problem Solving	Neuropsychological Assessment Battery (NAB): Mazes

Social Cognition

To assess emotional processing, the Managing Emotions component of the Mayer-Salovey-Caruso Emotional Intelligence Test (MSCEIT; [57]) will be administered. Managing Emotions has 2 subscales that examine the regulation of emotions in oneself and in one's relationships with others. These subscales include vignettes of various situations, along with ways to cope with the emotions depicted in these vignettes. Subjects are required to indicate the effectiveness of each solution, ranging from 1 (very ineffective) to 5 (very effective). It takes about 15 min to complete this measure.

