In addition to this high-level social cognitive test, a low-level social cognitive test, the Affective Prosody Task (APT; [58]), will be used to measure auditory emotion recognition. Stimuli consist of audio recordings of semantically neutral sentences spoken with different voice tones. The sentences are either statements or questions and conveyed in 6 emotions (fear, anger, happiness, sadness, disgust, or neutral). After each stimulus, a list of the 6 possible choices is presented on the computer screen and the participant selects one emotion. It takes about 15 min to complete this task.

A social cognitive composite score will be created by standardizing (z-scoring) then summing the total scores from the MSCEIT Managing Emotions subtest and the APT. The social cognitive composite score will be included in exploratory analyses.

Functional Capacity and Community Functioning

To assess functional capacity, the UCSD Performance-based Skills Assessment (UPSA; [59]) will be administered. The UPSA assesses five skill areas that are considered essential to functioning in the community: General Organization; Finance; Social/Communications; Transportation; and Household Chores. The UPSA involves role-play tasks with props that are administered in the laboratory as simulations of events that the person may encounter in the community. These tasks are similar in complexity to situations that a community-dwelling person with chronic mental illness is likely to encounter. Inter-rater reliability of ratings are excellent (intraclass correlation coefficient = .91, $p < .001$). The UPSA takes 25 minutes to administer and yields a total score and domain scores. The UPSA total score will serve as the primary functional outcome measure.

To assess community functioning, the Role Functioning Scale (RFS; [60]) will be administered. The RFS assesses patients' current level of functioning in four areas: independent living skills, social (both family and non-family) functioning, and work functioning. The subscale ratings range from 1 (severely impaired) to 7 (maximal functioning) and include anchor points that detail both the quantity and quality of functioning. The RFS will be administered as part of an approximately 30-minute interview and rated by one of several trained interviewers in our lab. The RFS yields a total score and domain scores.

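### The plan seeks the domains that drive an MCCB or UPSA effect through separate subscale models and never tests whether effects differ between domains

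*Combined protocol and SAP*

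**What the plan says.** Three places give the subscale analyses the same purpose.

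- Behavioral Assessments, Neurocognition: the MCCB domain scores are for secondary analyses "to determine whether an overall effect is driven by any particular aspect of neurocognition". The composite is built from the same scores: "The remaining 6 domain t-scores from the MCCB will be averaged to create a composite score".
- Statistical Plan: "If significant treatment effects are found on any of the primary outcomes, we will perform secondary analyses on the corresponding components or subscale scores", with the aim "to determine whether the results are driven by particular aspects of the main constructs". On error control: "All results will therefore be reported using an uncorrected two-sided significance level" of .05.
- Analysis Plan By Specific Aim, Exploratory Analyses: a significant global measure is followed by "equivalent models for the component subdomain scores to identify the primary drivers of treatment effects".

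The model to be repeated is the core model under Primary Analyses. It has group as the between-subject factor, "time (baseline, end of treatment) as the within subject factor, and a group by time interaction". It has no domain factor.

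The UPSA is handled the same way: "The UPSA assesses five skill areas that are considered essential to functioning in the community". For MMN amplitude at Fz no subscales are listed, so the point concerns the MCCB and the UPSA.

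**The concern.** To say that one domain drives an effect is to say that domains differ. Separate models test each domain against zero. If verbal memory gives p = .03 and working memory p = .10, the two effects may still be equal; the comparison between them has not been made. Requiring a significant composite first does not help, because the faulty step comes after it. Nor would correcting the six p-values, because they would still be tests against zero.

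The Statistical Plan says the study should help select intervention components and measures for a later definitive trial. A driver picked out by sampling noise could steer that choice. It could also colour the bottom-up versus top-down interpretation, since the background chooses auditory training partly because verbal learning and memory tend to be the most impaired domain. A chance verbal-memory finding would look like support for the theory.

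**Working it through.** **Inputs from the documents.** Completers are 38, 38 and 19 (Randomization and Treatment Procedure). The active-arm contrast is d = .5 after treatment with none at baseline, with within-subject correlation r = .7 and two-sided α = .05 (Power Considerations). There are six MCCB domains and five UPSA areas.

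**Input assumed.** The correlation ρ of change scores between domains is not in the documents, so it is varied. Domains are taken as equally correlated with equal SD.

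**Step 1: reproduce the plan's power.** With two time points, the group by time contrast is a comparison of mean changes.

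- SD of change = √(2(1 − .7)) = .775 baseline SD.
- Standard error = .775 × √(2/38) = .178.
- .5/.178 = 2.81, so power ≈ Φ(2.81 − 1.96) = .80.

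This agrees with the plan, which calls power for this contrast sufficient and uses 80% for its neighbouring statements.

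**Step 2: the same effect in every domain.** The mean of six equally correlated domains has SD √((1 + 5ρ)/6) times that of one domain. A composite d of .5 therefore corresponds to a per-domain effect δ = .5 × √((1 + 5ρ)/6).

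- ρ = .3: δ = .5 × √(2.5/6) = .32
- ρ = .5: δ = .5 × √(3.5/6) = .38
- ρ = .7: δ = .5 × √(4.5/6) = .43

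**Step 3: count significant domains among simulated trials with a significant composite.** All domains have the same true effect.

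| ρ | Power, one domain | Some but not all of 6 significant | All 6 significant | Only 1 or 2 significant |
|---|---|---|---|---|
| .3 | 44% | about 92% | 6% | about 35% |
| .5 | 56% | about 75% | 24% | 18% |
| .7 | 68% | about 50% | 50% | about 8% |

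For five UPSA areas the some-but-not-all rate is 88%, 71% and 46% at the same three values of ρ.

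**Step 4: sensitivity (six domains).**

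- At d = .5 the rate falls to 36% at ρ = .8 and 22% at ρ = .9.
- At d = .7 it is 74% (ρ = .3) and 43% (ρ = .5).
- At d = 1.0 it is 23% (ρ = .3).
- At d = .3 it is 95% (ρ = .3) and 75% (ρ = .7).

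**Step 5: direct tests under the same uniform effect.** False-driver rate given a significant composite:

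- Joint test of the five differences among domains (Hotelling T², equivalent to group by time by domain): about 5%.
- Six domain-versus-mean-of-the-rest contrasts, Bonferroni-adjusted: about 5%.
- Driver named if the joint test **or** any unadjusted contrast is significant: about 25%.

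**Step 6: power when one domain truly differs (ρ = .3 to .5).**

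| True effects | Joint test | Contrast for one domain named in advance |
|---|---|---|
| .8 SD in one domain, .2 in five | about 78% to 92% | 95% to 99% |
| .6 SD in one domain, .3 in five | about 22% to 33% | 44% to 57% |

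**The case against.** **The decision rule is inferred.** A reader might take the plan to say that a significant domain is a driver. It does not say so. It describes itself as estimating treatment effects, and comparing effect sizes across domains would also fit the text. This stands as a limit on the wording. It does not remove the gap: no comparison between domains and no rule for naming a driver is given, and the .05 threshold is the only criterion in sight.

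**The size depends on an unstated correlation.** A reader might infer that a uniform effect will usually be reported as driven by one domain. The documents do not support that. The mixed pattern is about as likely as not at ρ = .7 and is the minority outcome above it or with large true effects. A mixed pattern also includes five significant domains out of six, which few would call a driver. The more suggestive pattern of one or two significant domains occurs in about 35%, 18% and 8% of trials at ρ = .3, .5 and .7. Both limits stand.

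**The analyses are exploratory.** They are labelled secondary or exploratory, run only after a significant primary result, and belong to a study that calls itself preliminary and does not want to overlook a relevant outcome. That justifies a lenient threshold. It does not justify drawing a conclusion from a test of a different question, and describing every domain with its interval keeps all of them in view.

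**A direct test is weak here.** For a twofold difference between domains it will usually miss. This is true, and it is a reason for restraint in naming drivers.

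**Conclusion.** The concern holds as a point about interpretation. The plan intends to say which domains drive an effect, and its method cannot show that domains differ. At the plan's own design values, an effect equal in all six MCCB domains yields a mixed set of significant and non-significant domains in about 92%, 75% and 50% of trials with a significant composite (ρ = .3, .5, .7). These figures rest on an assumed, equal correlation of change between domains and on a true composite effect of d = .5. They fall with higher correlation or a larger effect.

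A reader might go further and conclude that the trial's main findings are compromised. They are not: the primary contrasts, their error rate and the sample size do not depend on these models. The change should be made, but it affects only the secondary and exploratory reading.

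**What to change.** Amend Statistical Plan and Exploratory Analyses, and align the sentence under Neurocognition.

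1. After a significant composite, fit one model per construct with domain as an added within-subject factor: the six MCCB T-scores, or the five UPSA areas each scaled by its baseline SD.
2. Use driver language only if group by time by domain is significant at .05, then locate the difference with contrasts of each domain against the mean of the others.
3. As an alternative to step 2, use those contrasts alone with Bonferroni or Holm adjustment (Bonferroni: .05/6 = .0083 for the MCCB, .05/5 = .01 for the UPSA), or test a single domain named in advance.
4. Do not accept either the joint test or any unadjusted contrast as sufficient; that rule brings the false-driver rate back to about 25%.
5. Report all single-domain estimates with confidence intervals, as description.

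The cost is SAP wording and one extra model per construct on data already planned. Fewer drivers will be declared, and the SAP should say so: power of the joint test is good for a fourfold difference between domains and poor for a twofold one.
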